4.3.2.3.1. Genotype

At screening HIV-1 PR/RT genotype will be assessed by the GenoSureMGTM assay. Post-screening HIV-1 PR/RT genotype/phenotype will be assessed by the PhenoSenseGTTM assay.

Evaluation of screening and treatment-ermergent RAMs will be based on PI, N(t)RTI, and NNRTI mutation lists defined by IAS-USA. RAMs were considered treatment-emergent if they were detected post-baseline but not at screening/baseline. Individual listings will be generated. Genotypes will be shown per region (PR and RT), time point and treatment phase. Mutations will be marked by lists and if they emerged.

At screening, a tabulation per treatment group will present the number of patients with a specific mutation or number of patients with at least one PR or RT mutation belonging to a specific mutation list (see below). Percentages and the mean/median will be calculated based on the number of subjects with screening genotypes.

Post baseline, a tabulation of emerging mutations per treatment group will present the number of patients with a specific emerging mutation or number of patients with emerging mutations belonging to a specific mutation list (see below).

The analysis assumes a worst-case scenario in case of multiple post-screening sequencing results: if any of a patient's samples shows a mutation, the patient is assumed to have this mutation, even if other samples show wild-type virus. The percentage of patients with emerging mutations will be calculated on the number of patients with paired screening/baseline and post-baseline genotypes and on all ITT patients. The denominator should be shown.

All analyses will be conducted on the Efficacy ITT population, unless specified otherwise, and will be presented by "all patients with available post baseline genotypes" and by "protocol defined virologic failure with post baseline genotypes", taking into account either "all genotypes" or only the "genotypes that are on-treatment".

Protease mutations

- IAS-USA³ Primary PI mutations (n=23)
 D30N, V32I, M46I/L, I47A/V, G48V, I50L/V, I54L/M, Q58E, T74P, L76V, V82A/F/L/S/T, N83D, I84V, N88S, L90M
- IAS-USA³ Secondary PI mutations (n=52)
 L10C/F/I/R/V, V11I, G16E, K20I/M/R/T/V, L24I, L33I/F/V, E34Q, M36I/L/V, K43T, F53L/Y, I54A/S/T/V, D60E, I62V, L63P, I64L/M/V, H69K/R, A71I/L/T/V, G73A/C/S/T, V77I, V82I, I85V, N88D, L89I/M/V, I93L/M
- IAS-USA³ DRV resistance-associated mutations (n=11)
 V11I, V32I, L33F, I47V, I50V, I54L/M, T74P, L76V, I84V, L89V

RT mutations

- IAS-USA³ NRTI resistance-associated mutations (n=22)
 M41L, A62V, K65R/E/N, D67N, 69ins, K70E/R, L74V, V75I, F77L, Y115F, F116Y, Q151M, M184I/V, L210W, T215F/Y, K219E/O
- IAS-USA³ NNRTI resistance-associated mutations (n=34)
 V90I, A98G, L100I, K101E/H/P, K103N/S, V106A/I/M, V108I, E138A/G/K/Q/R, V179D/F/L/T, Y181C/I/V, Y188C/H/L, G190A/S, H221Y, P225H, F227C, M230I/L
- IAS-USA³ Thymidine Analogue Mutations (TAMs) (n=8) M41L, D67N, K70R, L210W, T215Y/F, K219Q/E
- IAS-USA³ TFV resistance-associated mutations K65R/E/N, K70E
- IAS-USA³ FTC resistance-associated mutations K65R/E/N, M184I/V

4.3.2.3.2. Phenotype

Predicted phenotype based GenoSureMGTM, in-vitro phenotype data, and the overall resistance assessments based on the PhenoSenseGTTM assay will be presented in individual patient listings per drug and time point, if available.

If available, fold change (FC) in 50% effective concentration (EC₅₀) of ARVs versus wild-type HIV-1 virus will be included in individual listings per drug and time point.

When one cut-off value is available, a drug is considered

- Sensitive if the FC is below or equal to the clinical cut-off (CCO) when available or below or equal to the biological cut-off (BCO) otherwise;
- Resistant if the FC is above the clinical or biological cut-off.

When two cut-off values are available, a drug is considered

- Sensitive if the FC is below or equal to the lower cut-off;
- Partially sensitive if the FC is above the lower cut-off and below or equal to the higher cut-off;
- Resistant if the FC is above the higher cut-off.

If paired genotype or phenotype data are available loss of genotypic or phenotypic ARV susceptibility will be analyzed. Loss of susceptibility is defined as being "sensitive" at baseline (for genotype and phenotype) to "partially sensitive" (phenotype) or "resistance possible" (genotype) or "resistant" at post-baseline (for genotype and phenotype). Loss of susceptibility will be tabulated (numbers and proportions) per class and individual ARV. All analyses will be conducted on the Efficacy ITT population, unless specified otherwise, and will be presented by "all patients with available post baseline genotype/phenotypes" and by "protocol defined virologic failure with post baseline genotype/phenotypes", taking into account either "all genotypes/phenotypes" or only the "genotypes/phenotypes that are on-treatment".

BCOs and CCOs for the PhenoSense® GT Phenotyping Assay

Class	Drug	Generic name	Cut-off PhenoSense GT TM (V7045/V7145)
NRTI	AZT	Zidovudine	1.9
	3TC	Lamivudine	3.5
	ddI	Didanosine	1.3 - 2.2
	d4T	Stavudine	1.7

	ABC	Abacavir	4.5 – 6.5
	FTC	Emtricitabine	3.5
	TDF	Tenofovir	1.4 - 4.0
NNRTI	NVP	Nevirapine	4.5
	DLV	Delavirdine	6.2
	EFV	Efavirenz	3.0
	ETR	Etravirine	2.9 - 10.0
	RLP	Rilpivirine	2.0
PI	ATV	Atazanavir	2.2
	ATV/rtv	Boosted Atazanavir	5.2
	DRV/rtv	Boosted Darunavir	10.0 - 90.0
	APV/rtv or fAPV/rtv	Boosted Amprenavir or fosamprenavir	4.0 - 11.0
	IDV/rtv	Boosted Indinavir	10.0
	LPV/rtv	Boosted Lopinavir (Kaletra)	9.0 - 55.0
	NFV	Nelfinavir	3.6
	RTV	Ritonavir	2.5
	SQV/rtv	Boosted Saquinavir	2.3 - 12.0
	TPV/rtv	Boosted Tipranavir	2.0 - 8.0

Clinical cut-offs are shown in bold; cutoffs are based on the PhenosenseGT algorithm version 13

5. SAFETY

For initial D/C/F/TAF, periods "Baseline to Week 48", "Week 48 to Week 96" and "Baseline to Week 96" will be presented in the tables. For the late switchers, periods "Baseline to Switch" and "Switch to Week 96" will be presented.

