1.2. Trial Design

This is a randomized, double-blind active-controlled, multicenter, Phase 3 study to evaluate efficacy and safety of D/C/F/TAF once daily fixed dose combination regimen versus a regimen consisting of DRV/COBI FDC combined with FTC/TDF FDC in ARV treatment-naïve HIV-1 infected adult subjects.

The aim of this study was to include 670 subjects that were to be randomly assigned with 335 subjects planned per treatment group. Subjects who met all eligibility criteria were randomized in a 1:1 ratio to 1 of the following 2 treatment arms:

- D/C/F/TAF Arm: Regimen of a single tablet containing DRV 800 mg/ COBI 150 mg/

FTC 200 mg/ TAF 10 mg (D/C/F/TAF FDC) once daily, (n=335)

+ DRV/COBI FDC-matching and FTC/TDF FDC-matching placebo tablets

once daily;

- Control Arm: Regimen of DRV 800 mg/ COBI 150 mg FDC coadministered with FTC

200 mg/TDF 300 mg FDC once daily, (n=335)

+ D/C/F/TAF FDC-matching placebo tablet once daily.

Randomization was stratified by HIV-1 RNA level (\leq 100,000 copies/mL or \geq 100,000 copies/mL) and by CD4+ cell count (\leq 200 cells/ μ L or \geq 200 cells/ μ L) at screening.

Subjects will be treated for 96 weeks, and will return for study visits at Weeks 2, 4, 8, 12, 24, 36, 48, every 12 weeks thereafter until and including a Week 96 visit.

After Week 48, subjects will continue to take their blinded study drug and attend visits every 12 weeks until all subjects have reached Week 48, the database for the primary analysis has been locked, and treatment assignments have been unblinded. Provided the results from the primary analysis do not preclude (further) exposure of subjects to D/C/F/TAF, all subjects will return for an unblinding visit and will receive the D/C/F/TAF FDC tablet treatment during an open-label single-arm treatment phase up to Week 96. Subjects from the control arm who switch to the D/C/F/TAF regimen after the 48-week double-blind treatment will be required to return to the clinic for an additional visit 3 to 7 weeks after the unblinding visit.

After Week 96, subjects will be given the opportunity to continue D/C/F/TAF treatment during an extension phase until the D/C/F/TAF FDC tablet becomes commercially available and is reimbursed, or can be accessed through another source in the country where he/she is living, or until the sponsor terminates clinical development. During the extension phase subjects will attend visits every 6 months.

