1.5. Randomization and Blinding

Randomization

Central randomization was implemented in conducting this study. Subjects were assigned to 1 of 2 treatment groups in a 1:1 ratio based on computer-generated randomization schedule implemented in the interactive web response system (IWRS) before the study. Randomization minimizes the imbalance in the distribution of the number of subjects across treatment groups within the levels of each individual stratification factor: HIV-1 RNA level ($\leq 100,000$ copies/mL or > 100,000 copies/mL) and CD4+ cell count (< 200 cells/ μ L or ≥ 200 cells/ μ L) at screening. Based on the algorithm, the IWRS assigned a unique treatment code, which dictated the treatment assignment and matching study drug kit for the subject.

Blinding

Subjects continued to take their blinded study drug and to attend visits every 12 weeks following Week 48 until treatment assignment was unblinded. After unblinding, all subjects will receive D/C/F/TAF treatment during a single-arm treatment phase up to Week 96. Subjects from the control arm who switch to the D/C/F/TAF regimen after the 48-week double blind treatment were required to return to the clinic for an additional visit 3 to 7 weeks after the unblinding visit.

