2.2. Visit Windows

2.2.1. Trial Phases

Phases will be constructed for each subject as follows for adverse events, concomitant therapies, and for the determination of the worst-case/toxicity/change in the cross-tabulations.

Trial phase	Start date	End date
Screening	Minimum of Date of signing the informed consent and Date of the screening visit	1 day before start of treatment
Comparative	Date of the first intake (after	For ongoing subjects, in order of priority:
Treatment Phase	randomization)	- Week 48 visit date;
		if missing then;
		 Projected Week 48 visit date, where projected Week 48 visit date = baseline visit date + (7 *48)
		In case of withdrawal use:
		 Minimum(last intake date of study drug, study withdrawal date) +2 days
	Comparative treatment phase	If a subject switches prior to Week 96:
	end date +1 day	 Minimum(Date of last double-blind intake +2 days, Start Date of first Open Label D/C/F/TAF intake)
		If a subject never switches prior to Week 96:
		- Week 96 visit date;
		if missing then;
		 Projected Week 96 visit date, where projected Week 96 visit date = baseline visit date + (7 *96)
		In case of withdrawal prior to switching use:
		Minimum (last intake date of study drug, study withdrawal date) + 2 days
Single Arm	Extended double-blind	- Week 96 visit date;
treatment phase (Switch	treatment phase end date +1 day	if missing then;
to Week 96) *		 Projected Week 96 visit date, where projected Week 96 visit date = baseline visit date + (7 *96)
		In case of withdrawal after switch use:
		 Minimum (last intake date of study drug, study withdrawal date) + 2 days
Follow-up	Maximum (end date of extended double-blind treatment phase, end date of single arm treatment phase) +1 day	Trial termination date for all groups (date of last contact)

^{*} The 3-7 WEEKS AFTER UNBLINDING visit will be handled as follows:

Data up to each subject's Week 96 visit are in scope for this analysis; in addition DXA data (DP domain) up to Week 96 visit+28 days, and if applicable, any (confirmatory) viral load or genotype/phenotype results immediately subsequent to Week 96 (up to 6 weeks) will also be included in this analysis.

⁻ All efficacy assessments collected at this visit will be attributed to the DRV/COBI FDC + FTC/TDF FDC regimen

⁻ All safety assessments collected at this visit will be attributed to the D/C/F/TAF FDC regimen

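### In the Week 96 SAP the period-based safety tables give the two randomised arms no common period, so the blinded comparison cumulative to the switch is not shown and percentages for periods of unequal length stand side by side

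*SAP*

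**What the plan says.** The display rule is in SAP section 5. For one arm: "For initial D/C/F/TAF, periods 'Baseline to Week 48', 'Week 48 to Week 96' and 'Baseline to Week 96' will be presented in the tables". The control arm has its own list, in the sentence that opens "For the late switchers, periods": it names two periods only, one from baseline up to the switch and one from the switch up to Week 96.

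The design gives both arms a shared blinded period beyond Week 48. SAP 1.5 says: "Subjects continued to take their blinded study drug and to attend visits every 12 weeks following Week 48 until treatment assignment was unblinded". SAP 2.2.1 then builds trial phases subject by subject: "Phases will be constructed for each subject as follows for adverse events, concomitant therapies", and for the worst-case and toxicity cross-tabulations. For a subject who switches before Week 96, the phase after the comparative phase ends at "Minimum(Date of last double-blind intake +2 days, Start Date of first Open Label D/C/F/TAF intake"). A separate rule covers the other case, "If a subject never switches prior to Week 96". Neither rule is restricted to one arm.

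Other sections already use the switch date or align the arms. SAP 2.4.1 and 3.3 split adherence at the switch, and 2.4.1 does so explicitly for the Initial arm. SAP 3.2 gives disposition from Baseline to Week 48 and from Baseline to Week 96 in both arms, and splits the Late Switch arm at Week 48 and at the switch. SAP 2.6 uses the original baseline as the safety reference in both arms before the switch.

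**The concern.** Several safety outputs accumulate over time and can only rise as the period lengthens: the share of subjects with a given adverse event (SAP 5.1.2), the worst toxicity grade (5.2.2), the minimum GFR stage (5.2.3.1), subclinical tubulopathy (5.2.3.2) and the worst vital-sign abnormality (5.3). For these, a between-arm reading needs the same window in both arms, and the section 5 lists provide none. The control arm's blinded time after Week 48 sits only inside Baseline to Switch. The Initial arm's blinded time after Week 48 is mixed with open-label time in its Week 48 to Week 96 column.

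Two things are at stake. First, protocol section 3.2 explains that the control regimen permits a direct TAF-versus-TDF safety comparison. The longest randomised, blinded form of it, from baseline to the switch, is not tabulated. Second, the nearest available columns differ in length, so a difference can appear between arms with identical risk.

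**Working it through.** The plan states no figure to reproduce here, and the point does not depend on sample size, power or alpha. The first step compares the period lists; the second shows how much unequal length can matter.

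**Period lists (SAP section 5)**

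| Period | Initial D/C/F/TAF | Control (Late Switch) |
|---|---|---|
| Baseline to Week 48 | shown | not shown |
| Baseline to Switch | not shown | shown |
| Week 48 to Week 96 | shown | not shown |
| Switch to Week 96 | not shown | shown |
| Baseline to Week 96 | shown | not shown |

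No row is filled in both columns.

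**Crude percentages**

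Assumptions, none of them from the documents: the same constant hazard in both arms, no withdrawals, and a single switch week S of 60, 72 or 84. If p is the incidence by Week 48, the incidence by week S is 1 − (1 − p)^(S/48). For p = 10% and S = 60 this is 1 − 0.9^1.25 = 12.3%. The last column uses a hazard of 0.5 per year, 1 − exp(−0.5 × S/52.18), which gives 36.9% at Week 48.

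| Period ends at week | p = 5% | p = 10% | 0.5 per year |
|---|---|---|---|
| 48 | 5.0% | 10.0% | 36.9% |
| 60 | 6.2% | 12.3% | 43.7% |
| 72 | 7.4% | 14.6% | 49.8% |
| 84 | 8.6% | 16.8% | 55.3% |
| 96 | 9.8% | 19.0% | 60.1% |

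Control Baseline to Switch minus Initial Baseline to Week 48, for S = 60, 72 and 84:
- p = 5%: 1.2, 2.4 and 3.6 points.
- p = 10%: 2.3, 4.6 and 6.8 points.
- 0.5 per year: 6.8, 12.9 and 18.4 points.

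With a switch at Week 52 and p = 10%, the gap is only 0.8 points (10.8% against 10.0%). Against the Initial arm's Baseline to Week 96 column the sign reverses: for p = 10%, control is lower by 6.7, 4.4 and 2.2 points. Which arm looks worse depends on the column chosen.

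**Exposure-adjusted rates (EAIR, SAP 5.1.2)**

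The SAP divides the number of subjects with events by summed exposure time and does not say whether exposure stops at the first event.
- If it stops there, a constant hazard gives the same rate in every column.
- If whole-period exposure is used, a constant hazard still gives little distortion for p = 10%: 0.109 per patient-year at Week 48 against 0.107, 0.106 and 0.105 at Weeks 60, 72 and 84. At 0.5 per year the figures are 0.401 against 0.380, 0.361 and 0.343.
- If the hazard falls over time, the adjustment overshoots. With all events before Week 48 and whole-period exposure, the control/Initial ratio is 48/S: 0.80, 0.67 and 0.57. If the hazard halves after Week 48 (p = 10%), the ratio is [1 − 0.9 × 0.9^((S−48)/96)]/S divided by 0.10/48: 0.89, 0.82 and 0.77.

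With no treatment difference, crude percentages can therefore count against control while the adjusted rates count in its favour.

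**The case against.** The strongest reply is that this SAP covers only the Week 96 analysis. The two-arm safety objectives in protocol section 2.1 run to Week 48, and that comparison belongs to the separate Week 48 analysis. The later objective is the long-term safety of D/C/F/TAF. Showing the Initial arm to Week 96, and control before and after its switch, suits that objective. No between-arm safety comparison was prespecified for Week 48 to the switch, adverse events are not formally tested, and every column carries its period label. All of this stands, and it limits the point to a gap in presentation.

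A reader might infer that the randomised safety comparison is lost altogether, or that all laboratory and renal results are affected. The documents support neither. Laboratory values, vital signs, renal biomarkers, urine protein and albumin ratios and phosphate excretion are summarised by visit (SAP 5.2.2, 5.2.3.2, 5.3.2) in common visit windows (2.2.2). Both arms therefore appear at Weeks 60, 72 and 84, although a growing share of control subjects may have switched by then.

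The EAIR is a genuine safeguard that works well when hazards are roughly constant. It is promised only where applicable, however; it applies to adverse events and not to worst-value tables, and it misleads when events cluster early. The vital-sign abnormalities are derived by trial phase (5.3.1), which shows that the dates are available, but section 5 still sets the periods displayed. None of these supplies a common period for the adverse event and worst-value tables.

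**Conclusion.** The point holds for the period-based safety tables of the Week 96 analysis: adverse event incidences, worst grades and abnormalities, minimum GFR and subclinical tubulopathy. What goes unreported is the randomised, blinded comparison cumulative to the switch. The Week 48 comparison and the primary efficacy conclusion are untouched.

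That the period lists do not match is a matter of text and needs no assumption. The numerical size does. It rests on equal constant hazards, no withdrawals and a switch at Week 60 to 84: about 2 to 7 points for an event with 10% incidence by Week 48, and about 7 to 18 points for one with 37%. A reader might take the larger range as the expected distortion. The documents do not support that, because they give neither event rates nor switch times, and many of the listed endpoints (deaths, serious events, individual preferred terms) may be much rarer. The change is worth making because it costs little, but it is not a threat to the trial's conclusions.

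**What to change.** In the period-based safety tables, add a Baseline to Switch column for the Initial D/C/F/TAF arm, ending at the end of the extended double-blind phase as SAP 2.2.1 defines it. Add a Baseline to Week 48 column for the control arm. State in section 5 that the matched Baseline to Switch columns are the ones for the descriptive between-arm comparison, for crude percentages and for EAIR. Subjects who withdraw or never switch contribute up to the end dates that SAP 2.2.1 already gives. The cost is extra table columns only: no new data, date derivation, test or alpha is needed.

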5.1. Adverse Events

5.1.1. Definitions

Reported AE parameters and grades are based on the Division of AIDS Table for Grading the Severity of Adult and Pediatric Adverse Events ("**DAIDS AE grading table**"). All AEs will be coded using MedDRA version 19.1.

Events of interest

The EOIs groups include a broad list of terms to identify potential cases. The list of all preferred terms belonging to each AEOI group is provided in Attachment 2. Upon further clinical evaluation additional EOIs might need to be added, and these will be documented in the DPS.

Since many of the terms used to identify potential cases are clinically non-specific, only those retrieved cases that upon medical review are specifically suggestive of /compatible with the AEs of special interest will be commented on in the CSR.

Adverse events of interest (AEOI) groups used for the safety analyses are the following:

- Renal AEOI (for PRT)

Subgroups: laboratory related events,

clinical events

- Bone AEOI (for fractures)

Subgroups: Osteomalacia,

Bone Loss/atrophy,

Fracture, possibly osteoporotic,

Fracture other,

Other Bone Events

- Dyslipidaemia AEOI
- Liver AEOI
- Hyperglycemia AEOI
- Pancreas AEOI
- Severe skin AEOI
- Rash AEOI
- Immune reconstitution inflammatory AEOI
- Coronary artery AEOI
- Ocular AEOI (for posterior uveitis)
- Lipodystrophy AEOI
- Cardiac conduction AEOI

Subgroups: Conduction defects,

Torsade de pointes/QT prolongation

Convulsion AEOI

Adverse Drug Reaction (ADR)

ADRs will be presented. A current list of all ADRs is in Attachment 3. In case multiple lists are available (US and EU definitions), ADRs will be tabulated separately per list.

5.1.2. Analysis Methods

A summary will be provided for the following treatment-emergent adverse events:

- any adverse events,
- serious adverse events,
- deaths due to AE,
- adverse events by toxicity grade (as well as AEs with toxicity grade at least 2 and AEs with toxicity grades 3 or 4),
- AEs at least possibly related to study medication,
- AEs for which the medication was temporarily/permanently stopped,
- serious adverse events that were at least possibly related to the medication.

Incidences of AEs for above mentioned analyses will also be presented by SOC and preferred term. A listing of all AEs will be provided. There will be no formal statistical testing.

Additionally, where applicable, the exposure adjusted incidence rates (EAIR) will be provided. EAIR is calculated as follows:

EAIR=n/\subsection to where n is the number of subjects with events, ti is subject's exposure time in patient-years Summary of events and incidence tabulations for individual adverse events will be provided for AEOI and also for ADRs.

AIDS defining illness based on WHO clinical staging will be tabulated.

The number and percentage of subjects who experienced fracture events (subgroups Fracture, possibly osteoporotic and Fracture other of the Bone AEOI for fractures) will be summarized by treatment group.

Selected safety endpoints will be explored by subgroups defined in section 2.4.2. Details for subgroup analyses of safety endpoints will be provided in the DPS.

5.2. Clinical Laboratory Tests

5.2.1. Definitions

Laboratory parameters of the following lab subcategories will be investigated. The results will be displayed grouping the tests as follows:

- General biochemistry:
 - blood: creatine phosphokinase, alpha-1 acid glycoprotein
 - urine/dipstick: blood, nitrite, leukocyte esterase
- Hematology: hematocrit, hemoglobin, platelet count, red blood cell count (RBC), white blood cell count (WBC), mean corpuscular volume (MCV), mean corpuscular hemoglobin (MCH) and mean corpuscular hemoglobin concentration (MCHC).

Hematology differential counts: basophils, eosinophils, lymphocytes, monocytes, neutrophils (counts and %).

Laboratory Events of Interest

- Pancreatic Parameters: total amylase, lipase
- Hepatic parameters:
 - ALT, AST, alkaline phosphatase (ALP), gamma glutamyl transferase (GGT), bilirubin (all types)
 - Urine/dipstick: bilirubin, urobilinogen
- Lipid parameters: cholesterol, HDL cholesterol (HDL-C) (all types), LDL cholesterol (LDL-C) (all types), TC/HDL, triglycerides; these will be analyzed overall irrespective of fasting status as well as restricted to results from fasting samples separately
- Glucose parameters will be analyzed overall irrespective of fasting status as well as restricted to results from fasting samples separately:
 - blood: glucose
 - urine/dipstick: glucose, ketones
- Renal parameters:

- blood: total protein, creatinine, blood urea nitrogen, uric acid, phosphorus, potassium, sodium, bicarbonate, chloride, albumin
- urine/chemistry: creatinine, sodium, phosphate, glucose, urine albumin, urine protein
- urine/dipstick: glucose, protein

Laboratory toxicities will be derived based on the DAIDS toxicity grading scale (see Protocol).

Note: Local lab results will not be used for the analyses.

